## **10.6 Record Retention**

The investigator will retain study records including source data, copies of case report forms, consent forms, HIPAA authorizations, and all study correspondence in a secured facility for at least 6 years after the study file is closed with the IRB and FDA.

In addition, the Clinical Trials Office (CTO) will keep a master log of all patients participating in the study with sufficient information to allow retrieval of the medical records for that patient. Please contact the CTO before destroying any study related records.

## **11 Endpoints**

### **11.1 Primary Clinical Endpoint**

The primary endpoint is Lumbar BMC measured by DXA at 1 year after HCT (adjusted for height, age, sex, Tanner stage and race).

### **11.2 Secondary Clinical Endpoints**

Other endpoints are:

- TBMC measured by DXA (adjusted for height, age, sex, Tanner stage and race).
- Estimated bone strength, total BMD, cortical BMD, and trabecular BMD of the left tibia and non-dominant radius measured by pQCT.
- Levels of markers of bone resorption (carboxy-terminal collagen crosslinks [CTX] and deoxypyridinoline [DPD]), and bone formation (procollagen type 1 N-terminal propeptide [P1NP] and OCN)
- RANKL, OPG, and RANKL/OPG ratio.
- Levels of cytokines including interleukin (IL)-6, IL-7, and tumor necrosis factor-alpha (TNF- $\alpha$ ).
- Body composition: body mass index (BMI) percentile, lean body mass, and body fat mass (from DXA) adjusted for height.

## **12 Statistical Considerations**

### **12.1 Sample Size**

Sixty (60) subjects total (30 each in the Control and Pamidronate groups) gives 80% power to detect a difference between groups of 0.75 standard deviations (SDs)

describing variation in LBMC within study group after adjusting for height, age, sex, Tanner score, and race. Adjusting for age and sex, this SD is 5-8g (46, 47); adjusting further for race and height should reduce this SD by about half (48-50). This gives a within-group SD of about 2.5-4g and a detectable difference of 2-3g. To have 60 evaluable subjects, 192 need to be screened to allow for a 50% consent rate, 10% death rate by Day 90, 20% death rate between Day 90 and Day 360, and 10% drop out after randomization.

Anticipated Enrollment Over Duration of Study

	Screen	Study Entry Day -14 a	Day 7	Day 14	Day 21	Day 90	Day 180	Day 270	Day 360
Total	192	96	96	96	96	86	86	86	60
University of Minnesota (UMN)	96	48	48	48	48	43	43	43	30
Fred Hutchinson Cancer Research Center	96	48	48	48	48	43	43	43	30
a Day 0 is the day of hematopoietic cell transplantation (HCT).									

According to data from 2011 to 2012, 36 allogeneic transplants have been performed at UMN and 37 have been performed at Fred Hutchinson Cancer Research Center. It is expected that screening 28 patients per year will be feasible for both sites.

It anticipated that enrollment will take 3.5 years.

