### **6.2 Randomization (Day 90 Post-HCT Visit +/- 14 days)**

Randomization to pamidronate (Pamidronate Group) or no pamidronate (Control Group) will occur at Day 90 (+/- 14 days) by the institutional study coordinator based on the randomization schedule developed by the study statistician and entered into OnCore.

A brief review of continuing eligibility will be done and subjects will not be eligible for randomization if one or more of the following are true:

- Vitamin D ( $D_2+D_3$ )  $<20$  ng/ml as use of pamidronate is contraindicated due to potentially higher risk of hypocalcemia. Levels should be measured within 14 days prior to randomization.\*\*†
- serum creatinine is  $> 2$  times the baseline value (at Study Entry) - perform within 14 days prior to randomization
- an investigational study drug or agent, including biphosphonates, Denosumab, or Teriparatide, was administered within the previous 4 weeks or is planned for use during study participation (Day 90 through Day 360)
- positive pregnancy test (performed within 14 days prior to randomization)
- Inability to successfully complete a DEXA scan
- the parent or adult patient refuse randomization
- disease relapse has occurred

The randomization will be stratified by age with 2 strata:  $< 10$  years old and  $\geq 10$  years old.

If the patient is ineligible for or refuses randomization, no further research related procedures or treatment will occur after the Day 90 visit; however permission to continue review of the patient's medical record through the Day 360 visit for routine clinical information is embedded within the consent form document. This information will be collected only if the patient continues care at the enrolling

institution. Patient care will be at the discretion of the treating physician(s) and independent of this study.

OnCore will automatically generate an email alerting key study personnel of the randomization (or lack of).

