## 12.4 Statistical Methods

The primary analysis will compare the Pamidronate and Control groups according to LBMC measured by DXA using all available Day 360 measurements and adjusting for height, age, sex, Tanner score, and race. The analysis will be a multiple linear regression; the primary predictor will be randomized treatment assignment and adjusters listed above. If preliminary analysis shows that LBMC measurements have a grossly non-Gaussian (non- normal) distribution, a transformation of LBMC will be analyzed, most likely  $\log_{10}$  LBMC Secondary analyses will include the following:

- The hypothesis that subjects randomized to pamidronate will have higher total BMD, cortical BMD, trabecular BMD, and estimated bone strength measured by pQCT at 1 year compared to subjects randomized to control (Aim 1 Hypothesis 2) will be tested by applying the foregoing analyses to outcomes measured by pQCT, namely bone strength, total BMD, cortical BMD, and trabecular BMD, but excluding height from the adjusters.
- The hypothesis that cytokine levels will increase rapidly in the first 3 weeks after HCT, preceding an increase in markers of bone resorption (Aim 2 Hypothesis 1) will be tested, for each cytokine, by using all available data for each child (up to 4 measurements from Day -14 to Day 21) and fitting a mixed linear model with a random intercept and time trend for each child and testing whether the average time trend differs from zero.
- The hypothesis that in the Control Group, increased cytokine levels and receptor activator of nuclear factor- $\kappa$ B ligand/osteoprotegerin ratio at 3 weeks will be associated with decreased BMC and BMD at 1 year after HCT (Aim 2 Hypothesis 2) will be tested using linear regressions with dependent variables being each of the BMC and BMD measures at Day 360 and predictors being changes in each of the cytokine levels and RANKL/OPG ratio (from Day -14 to Day 21).
- For the hypothesis that markers of bone resorption will increase in the first 3 months after HCT, will remain elevated until at least Day 180 in the

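### Section 12.1 has no step for children alive at Day 90 but not randomised, so 192 screened gives 60 evaluable only if that loss is at most 0.8% to 3.5%

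*Combined protocol and SAP*

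**What the plan says.** Section 12.1 sets the target: "Sixty (60) subjects total (30 each in the Control and Pamidronate groups"). The power claimed for this target, in the same section, is "80% power to detect a difference between groups of 0.75 standard deviations (SDs"). The effect is put into grams: "This gives a within-group SD of about 2.5-4g and a detectable difference of 2-3g".

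The recruitment figure follows: "To have 60 evaluable subjects, 192 need to be screened to allow for a 50% consent rate, 10% death rate by Day 90", with two further losses, 20% deaths between Day 90 and Day 360 and 10% drop-out placed explicitly after randomisation. The anticipated-enrolment table has 192 at screening, 96 from study entry to Day 21, 86 from Day 90 to Day 270, and 60 at Day 360.

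Section 6.2 repeats an eligibility review at Day 90: "subjects will not be eligible for randomization if one or more of the following are true". The grounds are low vitamin D, raised creatinine, a recent or planned investigational or prohibited agent, a positive pregnancy test, an unsuccessful DXA scan, relapse, and "the parent or adult patient refuse randomization". A child who is not randomised has no further research procedures, only chart review.

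Section 12.2 analyses randomised subjects, and section 7.7 describes an evaluable subject as one who has been randomised and, where applicable, has had at least one dose.

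**The concern.** The table's Day 90 figure is 96 × 0.9 = 86, so death is the only loss allowed before randomisation. Every survivor is then carried forward as if randomised. No other step can absorb the section 6.2 losses: consent comes earlier, drop-out is counted only after randomisation, and children who are not randomised cannot count towards the 60. In effect the plan sets this loss to 0%.

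The loss is built into the design. Section 6.2 makes provision for data on patients who are ineligible or refuse. According to the revision history, relapse and inability to complete the scan were added as grounds in revisions 4 and 9; both are in the current section 6.2, and section 12.1 has no matching step.

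At stake is the figure of 60 on which the stated power rests, or, if 60 is held fixed, the screening number and the 3.5-year accrual period.

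**Working it through.** **Inputs from the documents.** 192 screened, 50% consent, 10% death by Day 90, 20% death from Day 90 to Day 360, 10% drop-out after randomisation, 60 evaluable in two equal groups, effect 0.75 SD (all section 12.1); 28 screened per site per year at two sites for 3.5 years (sections 12.1 and 13.6).

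**Assumptions.** Two-sided 0.05, because the documents state no alpha. The share q of Day 90 survivors not randomised is unknown and shown as a range. Non-randomisation is taken as independent of later death and drop-out.

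**1. Reproducing the power.** With 30 per group the noncentrality is 0.75 / √(1/30 + 1/30) = 2.90. The noncentral t with 58 df gives 81.5%. Section 12.4 specifies the model ("The analysis will be a multiple linear regression; the primary predictor will be randomized treatment assignment"); allowing five one-df covariates (53 df) gives 81.4%. The normal approximation gives 82.8%. All fit the stated 80%. A one-sided test would give 89.0%, so the two-sided assumption fits better.

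**2. Reproducing the chain.** 192 × 0.5 × 0.9 = 86.4 alive at Day 90. Section 12.1 does not say how the last two losses combine:

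- additive: 86.4 × (1 − 0.20 − 0.10) = 60.5
- multiplicative: 86.4 × 0.80 × 0.90 = 62.2

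Working back from 60, the screening number is 60 / (0.5 × 0.9 × 0.70) = 190.5, so 191 (additive), or 60 / (0.5 × 0.9 × 0.72) = 185.2, so 186 (multiplicative). The additive reading is closer to the stated 192 and 60.

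**3. Break-even for 60 evaluable.** q = 1 − 60/60.48 = 0.8% (additive) or 1 − 60/62.21 = 3.5% (multiplicative). Out of 86.4 survivors that is about 0.7 or 3.1 children.

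**4. Break-even for 80% power.** By the t calculation, 58 evaluable gives 80.1% and 57 gives 79.4%. So q = 1 − 58/60.48 = 4.1% or 1 − 58/62.21 = 6.8%.

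**5. Effect of assumed rates.** Evaluable = 86.4 × (1 − q) × 0.70 or 0.72. Screening needed to keep 60 = 190.5 or 185.2, divided by (1 − q) and rounded up. Years = screening number / 56 per year. Each cell is additive / multiplicative.

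| q (assumed) | Evaluable from 192 | Power | Screened to keep 60 | Years |
|---|---|---|---|---|
| 0% | 60.5 / 62.2 | 81.8% / 82.9% | 191 / 186 | 3.40 / 3.31 |
| 5% | 57.5 / 59.1 | 79.8% / 80.9% | 201 / 195 | 3.58 / 3.48 |
| 10% | 54.4 / 56.0 | 77.5% / 78.7% | 212 / 206 | 3.78 / 3.67 |
| 15% | 51.4 / 52.9 | 75.1% / 76.3% | 225 / 218 | 4.00 / 3.89 |
| 20% | 48.4 / 49.8 | 72.4% / 73.6% | 239 / 232 | 4.25 / 4.13 |

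**6. Capacity.** 2 × 28 × 3.5 = 196 screened. Using all of it absorbs q = 1 − 190.5/196 = 2.8% or 1 − 185.2/196 = 5.5%.

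**The case against.** A reader might infer that the trial will miss 60, or that its 80% power is lost. The documents do not support that, for four reasons.

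- **No rate is given.** The stated figures reproduce from their own inputs. The fault is a missing input, not an arithmetic error. This stands.
- **Power is less sensitive than the count.** It stays at 80% down to 58 evaluable, and at q = 10% the shortfall is 1.3 to 2.5 points. This also stands, so the two thresholds should be kept apart.
- **192 is a projection, not a cap.** The target is written as 60 evaluable, and nothing says that screening stops at 192. More screening could restore 60. This stands too, but it moves the cost to accrual time, since a loss above 2.8% to 5.5% exceeds the planned capacity.
- **Non-randomisation may overlap with later death.** Children barred for relapse may be among those expected to die by Day 360. As an illustration, take q = 10% and assume that half of that group would have died anyway. Deaths among the randomised are then 17.28 − 4.32 = 12.96 of 77.76. Evaluable is 77.76 − 12.96 − 7.78 = 57.0 (additive) or 64.8 × 0.9 = 58.3 (multiplicative), with power of about 79–80%. The true overlap is unknown; the table's larger losses are the most exposed to it.

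The protocol also mitigates several grounds: vitamin D supplementation from admission (section 7.1), exclusion at enrolment of planned agents that interact with pamidronate or affect bone (5.2.10), optional sedation for scans (7.5) and a ±14-day window (6.2). These may lower the rate, but they do not address refusal or relapse, and none of them justifies an unstated 0%.

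**Conclusion.** The omission is certain from the text; its size is not. The chain reaches 60 only if at most 0.8% (additive) to 3.5% (multiplicative) of Day 90 survivors are not randomised, and stated power holds only to a loss of about 4% to 7%. At assumed losses of 10% to 20%, 192 screened gives about 48 to 56 evaluable and 72% to 79% power, or else 60 evaluable needs about 206 to 239 screened and 3.7 to 4.25 years. These figures rest on the assumed rates, two-sided 0.05, and independence of non-randomisation from later losses. The point deserves correction because the trial relies on the 192-to-60 figure and its margin is at most about three children.

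**What to change.** Add a step for children alive but not randomised at Day 90 to section 12.1 and to the enrolment table, with a stated rate. The rate recorded in OnCore is a natural source, since section 6.2 says the system sends a notice of randomisation or its absence. State whether the later losses are added or multiplied. Then do one of two things:

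- keep 192 screened, and restate the evaluable number with its power or detectable difference; or
- keep 60 evaluable, and restate the screening number and accrual time.

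The change is an edit to text and table and alters no clinical rule. The first option needs no extra patients, but at losses above about 4% to 7% the power falls below 80%. The second keeps the power but costs more screening and, above a loss of 2.8% to 5.5%, more than the planned 3.5 years.

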## 12.2 Subject Population(s) for Analysis

All randomized subjects will be included in the primary analysis according to their randomized treatment assignment, consistent with the principle of intention-to-treat.

## 12.3 Randomization Scheme

The randomization will be stratified by age with 2 strata, < 10 years old and  $\geq$  10 years old, with 2/3 of the planned enrollment in the < 10 stratum. These fractions roughly reflect the proportion of each age group in the target study population. This choice of age groups is also based on our recent data which patients <10 years are more likely to be more severely affected (51). Each site's randomization schedule will use permuted blocks of lengths 2 and 4 within each stratum, so the study groups at a site never differ in sample size by more than 2 patients in

each stratum. The block lengths of 2 and 4 are alternated at random to make it harder to predict future treatment assignments. Randomized treatment assignments will be issued on Day 90 using a method that conceals the assignment until it is issued.

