## 4 Study Design

This is a Phase 2, open-label, randomized, controlled clinical study of pediatric subjects (defined as  $\geq 1$  year, but  $\leq 20$  years of age) treated with pamidronate with calcium and vitamin D versus calcium and vitamin D alone following HCT.

All subjects will receive a supplemental dose of vitamin D (based on vitamin D (D2+D3) level) beginning upon admission to the hospital for the HCT and calcium if they are not meeting the recommended dietary allowance (RDA) or if their serum calcium is low (based on ionized calcium level). Refer to Section 7.3 for supplementation guidelines.

At the Day 90 post-transplant visit, subjects will be randomized to receive one of the following treatment plans through the Day 360 post-transplant visit:

- Control Group: continue determined vitamin D per day and calcium supplementation, as appropriate to meet the RDA requirement. Refer to Section 7.1 for supplementation guidelines.
- Pamidronate Group: continue determined vitamin D per day and calcium supplementation, as appropriate to meet RDA requirement, AND 3 single IV infusions of 1 mg/kg (to a max of 60 kg) pamidronate at 3-month intervals (Day 90, 180 and 270) post-transplant. Refer to Section 7.3 for supplementation guidelines

Laboratory evaluations, DXA, and pQCT will be performed at specified time points per section 8 to monitor safety and evaluate treatment efficacy.

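### In this open-label trial, printed blocks of 2 and 4 by site and age stratum make the next assignment guessable about 71–72% of the time (equal mix assumed); longer, undisclosed blocks would serve Section 12.3's aim better

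*Combined protocol and SAP*

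**What the plan says.** - Section 4 describes an "open-label, randomized, controlled clinical study", so the site sees each child's arm once it is assigned.
- Section 12.3: the schedule of each site "will use permuted blocks of lengths 2 and 4 within each stratum". The strata are age under 10 and age 10 or over, "with 2/3 of the planned enrollment in the < 10 stratum".
- Section 12.3 gives the reason for mixing lengths: "The block lengths of 2 and 4 are alternated at random to make it harder to predict future treatment assignments". It gives no mixing probabilities. It also states the balance obtained: "so the study groups at a site never differ in sample size by more than 2 patients" in each stratum. It says that each assignment is concealed until issued on Day 90, without naming the method.
- Section 6.2: randomization "will occur at Day 90 (+/- 14 days) by the institutional study coordinator", from a schedule that the study statistician prepared and that is held in OnCore. OnCore alerts key personnel to each randomization or non-randomization. A short review of continuing eligibility comes first; the text does not say who does it.

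**The concern.** Concealing the next list entry protects the allocation only if that entry cannot be inferred. Here three things combine: visible past assignments, a separate short list for each site and stratum, and block lengths printed in the site's own protocol. A block of 2 is the weakest element, because its second assignment is fixed by its first.

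Anyone at a site who keeps a tally by stratum could form a good guess before the next child is randomized. Some Day 90 conditions in Section 6.2 leave room for influence: refusal of randomization, inability to complete a DXA scan, and planned use of an investigational agent. The ±14 day window could also allow two children in the same stratum to be reordered.

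The primary model in Section 12.4 adjusts for height, age, sex, Tanner score and race. It does not include Day 90 lumbar bone mineral content, and glucocorticoid exposure for GVHD appears only among the exploratory risk factors. Selection on such factors would not be corrected by the planned analysis.

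**Working it through.** **Inputs.** Block lengths 2 and 4 by site and stratum, and the maximum difference of 2 (Section 12.3). Allocation 1:1 and 43 children per site at Day 90 (Section 12.1). Two thirds of 43 is 28.7, so the strata are taken as 29 and 14. The mix of lengths is not stated. **Assumption:** each block has length 2 or 4 with probability 1/2, independently; P(length 4) is then varied from 1/4 to 3/4.

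**The plan's own figure.** Under this scheme the largest difference within a site and stratum is 2, as Section 12.3 states.

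**Chance of guessing the next assignment.** The guesser knows the lengths and the past assignments, but not where blocks begin. Let P be the probability of length 4.

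1. Arms level: the guess is 50%.
2. Arms differ by 1 at the second place of a known new block: a block of 2 makes the lagging arm certain, and a block of 4 gives it 2/3. The chance is (1 − P) × 1 + P × 2/3 = 1 − P/3, which is 5/6 = 83.3% at P = 1/2.
3. Fourth child, when the first two split evenly and the third has made the arms unequal: the weights after two children are 0.5 × 1 = 0.5 (block of 2 finished) and 0.5 × 2/3 = 0.333 (middle of a block of 4), or 0.6 and 0.4. The chance for the lagging arm is 0.4 × 1 + 0.6 × 5/6 = 0.90.
4. Arms differ by 2: this occurs only inside a block of 4, so the next two assignments are certain.

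At P = 1/2, every even-numbered child in a stratum is therefore guessable at 5/6 or better, as is an odd-numbered child when the arms differ by 2. Among odd places, 1/3 lie in the middle of a block of 4, and in 1/3 of those the first two assignments match. The long-run share is 1/2 + (1/2)(1/3)(1/3) = 1/2 + 1/18 = 55.6%.

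**Finite strata, equal mix (exact recursion).** The expected number guessable with at least 80% confidence is 15.59 of 29 (53.8%) and 7.70 of 14 (55.0%). Per site this is 23.3 of 43 = 54.2%, or about 47 of 86 in all. Certain: 10.4%. A simulation of 40,000 replicates agrees. It shows that naming the lagging arm is right 89.7% of the time when the arms are unequal, so overall accuracy is 0.542 × 0.897 + 0.458 × 0.5 = 71.5%.

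**Sensitivity to the mix (per site, 29 + 14).**

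| P(length 4) | Guessable at ≥80% | Certain | Best guess right |
|---|---|---|---|
| 1/4 | 52.0% | 6.2% | 72.7% |
| 1/2 | 54.2% | 10.4% | 71.5% |
| 3/5 | 54.9% | 11.8% | 71.1% |
| 2/3 | 45.1% | 12.6% | 70.9% |
| 3/4 | 38.7% | 13.5% | 70.6% |

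The break comes where 1 − P/3 = 0.80, at P = 0.6. At P = 3/4 the two strata give 36.3% (14) and 39.9% (29).

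**Longer blocks, equal mix, strata of 14 and 29.**

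| Lengths | Guessable at ≥80% | Certain | Best guess right | Largest difference |
|---|---|---|---|---|
| 2, 4 | 54–55% | 10–11% | 71–72% | 2 |
| 4, 6 | 28–30% | about 6% | 68% | 3 |
| 4, 6, 8 | 18–22% | about 2% | 67% | 4 |

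**The case against.** **The mix is unknown.** This stands. A reader might infer that more than half of assignments are guessable with high confidence whatever the mix. The documents do not support that: the share passes one half only up to P(length 4) = 0.6, and 5/6 lies just above the 80% cut-off. Overall accuracy hardly depends on the mix (70.6% to 72.7% over the range shown).

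**There is little room to act.** Largely right. Consent is obtained before transplant (Sections 5 and 13.3), which closes the usual route of choosing whom to approach. Most Section 6.2 conditions are objective: vitamin D, creatinine, pregnancy test, relapse. Refusal belongs to the parent or adult patient. At 43 children per site over 3.5 years (43/3.5 = 12.3 a year, about one a month across both strata), chances to reorder are few. A reader might also infer that the coordinator who randomizes judges eligibility too, but Section 6.2 names no one for that review.

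**Selection would leave traces.** Also right. A reader might infer that any bias would be invisible and beyond adjustment. However, every child is registered before transplant, baseline measurements are scheduled at Study Entry (Section 8.1), and Section 6.2 allows record review through Day 360 for non-randomized children who stay in care at the site. Randomized and non-randomized children can therefore be compared, and selection on the model's covariates is at least partly adjusted. What remains is selection on factors outside the model.

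**The gain is modest.** On overall accuracy it is: from 71–72% to 67–68%. The gain lies in confident and certain guesses. The endpoint is an instrument measurement, which limits biased assessment but does not affect selection into the arms.

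**Conclusion.** The concern holds as a minor design weakness. Open-label treatment, site-specific lists and printed lengths of 2 and 4 let past assignments inform the next, despite concealment of the list entry. With an equal mix (an assumption), about 54% of assignments are guessable with at least 80% confidence, about 10% are certain, and the best guess is right 71–72% of the time. With three quarters of blocks at length 4, the first figure is about 36–40%. All these figures suppose that someone at the site tracks assignments by stratum.

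This is an opportunity, not a finding that selection took place; nothing in the documents shows that it did. The room to act is limited to the less objective Day 90 conditions and to ordering within the window. Selection on factors such as Day 90 bone status or steroid exposure would not be corrected by the planned analysis, but could be partly checked from baseline data.

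**What to change.** For any remaining assignments:

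- Generate new lists with lengths 4 and 6, or 4, 6 and 8, mixed at random.
- Hold the lengths and their probabilities in a document that only the statistician sees, and remove them from Section 12.3.
- Revise or delete the Section 12.3 sentence on the maximum difference of 2. It would no longer be true, and a stated maximum hints at the block length.

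**Cost.** New lists and a short amendment. The largest difference per site and stratum rises from 2 to 3, or to 4 with blocks of 8. Relative to equal arms, the efficiency of an unadjusted comparison of N children whose arms differ by d is 1 − (d/N)². Even if all four site-strata reached their maximum in the same direction among 86 children, this is 1 − (8/86)² = 99.1% now, 1 − (12/86)² = 98.1% with lengths 4 and 6, and 1 − (16/86)² = 96.5% with 4, 6 and 8. Age is already in the primary model.

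**Limit.** The current text is Revision 10 (July 2019), and Revision 1 (October 2014) preceded the start of enrollment, which was planned to last 3.5 years. The documents do not show how many assignments remain. If none do, what is left is the check: compare randomized and non-randomized children on baseline data, and set each non-randomization against the preceding assignments in its site and stratum.
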